### **12.2 Sample Size Justification**

The sample size will be 110 subjects due to early study termination.

### **12.3 Study Populations**

Two populations will be employed in the analysis of study data:

- The modified intent-to-treat (mITT) population will consist of all subjects who are randomized and take at least 1 dose of study drug. All safety analyses will be performed on the mITT population. The Evaluable for Efficacy population will consist of subjects who have non-missing baseline and Week 16 PASI scores and do not have a major protocol violation.

Demographics, subject disposition, and screening and baseline characteristics will be summarized for mITT populations, where appropriate.

### **12.4 Subject Accountability, Demographics, and Baseline Characteristics**

Subject disposition will be tabulated by treatment group. Similarly, subject demographic information and baseline characteristics will be displayed.

### **12.5 KD025 Exposure**

The amount of KD025 administered by visit and overall will be tabulated by treatment group and presented by subject in data listings. In addition, delays and all other alterations in KD025 administration will be presented.

### **12.6 Concomitant Medications**

Concomitant medications will be coded using WHO Drug Dictionary and the data will be summarized by treatment and presented in tables and listings.

### **12.7 Efficacy Analysis**

The primary efficacy endpoint for analyses will be the number (%) of subjects with a 75% decrease in PASI by Week 16.

The secondary efficacy endpoints for analysis will include the following:

1. A 50% reduction in Week 16 PASI score (PASI 50)
2. The mean Week 16 percent change from baseline in PASI
3. Improvements in PGA of “clear” or “almost clear” at Week 16
4. Improvements in DLQI at Week 16

The exploratory efficacy endpoints are:

- To evaluate the concentration and changes in IL-17 expression in blood, tissue, and other biomarkers in punch biopsies after 16 weeks of dosing with KD025

Efficacy analyses will be divided into 2 periods: the double-blind treatment period through database lock at Week 16 and the open-label, 32-week continuation period.

Efficacy analyses will include the number (%) of subjects with a 75% decrease in PASI (number of subjects that reach PASI 75) at Week 16 in the KD025 treatment groups compared with the placebo group in a pairwise manner using a Fisher’s Exact test. The number of subjects who reach PASI 50 at Week 16 will be analyzed similarly. Treatment group differences in DLQI and PGA changes from baseline to Week 16 will be assessed using an analysis of covariance (ANCOVA) model with treatment as a fixed effect and a subject’s baseline value as a covariate.

No adjustments for multiplicity are being made for this Phase 2 study.

For further details, see the statistical analysis plan (SAP).

## 12.8 Safety Data

Safety assessments will include AEs, SAEs, PEs (including weight), vital sign measurements (including BP, pulse rate, respiratory rate, and temperature), clinical laboratory evaluations (hematology, chemistry, urinalysis, coagulation, lipid panel, TSH) ECGs, and reasons for treatment discontinuation due to toxicity.

The primary safety endpoint will be the percentage of subjects in each treatment group experiencing AEs.

TEAEs will be summarized by treatment group using MedDRA® SOC and preferred term, classified from verbatim terms (Version 18.1 or higher). The incidence and percentage of subjects with at least 1 occurrence of a preferred term will be included, according to the most

severe grade using a 5-point scale (mild, moderate, severe, life threatening, or death). The number of events per preferred term will also be summarized. Causality (relationship to study treatment) will be summarized separately.

AEs, SAEs, related AEs, related SAEs,  $\geq$  Grade 3 AEs, related  $\geq$  Grade 3 AEs, and AEs leading to withdrawal or treatment discontinuation will be summarized by treatment group according to SOC and preferred terms. AEs will also be presented in listings. Duration of AEs will be determined and included in listings, along with action taken and outcome.

Laboratory results will be classified using the Toxicity Grading Scale for Healthy Adult and Adolescent Volunteers Enrolled in Preventive Vaccine Clinical Studies (see Appendix A) and summarized. Incidence of laboratory abnormalities will be summarized by treatment group. The worst on-study grade after the first dose of study drug will be summarized by treatment group. The incidence of  $\geq$  Grade 3 laboratory abnormalities under treatment and shifts in toxicity grading from baseline to highest grade post-baseline will be displayed.

Vital sign measurements will be summarized at each scheduled time point using descriptive statistics.

### **13 DATA QUALITY ASSURANCE**

Accurate and reliable data collection will be ensured by verification and cross-check of the eCRFs against the investigator's records by the study monitor (source document verification) and by the maintenance of a drug-dispensing log by the investigator. Collected data will be entered into a computer database and subject to electronic and manual quality assurance procedures.

## **14 ETHICAL ASPECTS**

### **14.1 Local Regulations**

The study must fully adhere to the principles outlined in “Guideline for Good Clinical Practice” ICH E6 Tripartite Guideline (January 1997), and in general, be conducted in a manner consistent with the most recent version of the Declaration of Helsinki. The investigator will ensure that the conduct of the study complies with the basic principles of GCP as outlined in the current version of 21 CFR, subpart D, Part 312, “Responsibilities of Sponsors and Investigators”, Part 50, “Protection of Human Subjects”, and Part 56, “Institutional Review Boards”.

### **14.2 Informed Consent Form**

Sample ICFs will be supplied to each site. Kadmon or its designee must review any ICF prior to submission for review by the IRB. The final IRB-approved document must be provided to Kadmon for regulatory purposes.

It is the responsibility of the investigator, or a person designated by the investigator, to obtain a written ICF from each subject (or the subject’s legally authorized representative) agreeing to participate in this study after adequate explanation of the aims, methods, anticipated benefits, and potential hazards of the study in accordance with federal and state regulations is provided. In the case where the subject is unable to read, an impartial witness should be present during the entire ICF discussion. After the subject has orally consented to participation in the study, the witness’ signature on the form will attest that the information in the consent form was accurately explained and understood. A copy of the ICF must be provided to the subject or to the subject’s legally authorized representative. If applicable, it will be provided in a certified translation of the local language.

The eCRF for this study contains a section for documenting informed subject consent, and this must be completed appropriately. Signed ICFs must remain in each subject’s study file and must be available for verification by study monitors at any time. If new safety information results in changes in the risk/benefit assessment, the consent form should be reviewed and updated as necessary. All subjects (including those already being treated) should be informed of the new

information, should be given a copy of the revised form, and should give their consent to continue in the study.

#### **14.3 Institutional Review Board**

This study is being conducted under a US IND application. This protocol (and any modifications) and appropriate consent procedures must be reviewed and approved by an IRB. This board must operate in accordance with the current federal or local regulations. The investigator will send a letter or certificate of IRB approval to Kadmon (or designee) before subject enrollment and whenever subsequent modifications to the protocol are made.

#### **14.4 Future Use of Subject Samples**

Not all of the tissue and blood components obtained during this study may be required for the tests that are part of the clinical study. Following the conclusion of the study, the samples may be used for additional research. This research will help to understand disease subtypes, drug response and toxicity, and possibly identify new drug targets or biomarkers that predict subject response to treatment. The use of the samples for internal research will be done according to the guidelines defined by the FDA guidance for In Vitro Diagnostic Device Studies Using Leftover Human Specimens that are Not Individual Identifiable (issued 25 April 2006) and the European Medicines Agency (EMA) Reflection Paper on Pharmacogenetic Samples, Testing and Data Handling (EMA/CHMP/PGxWP/201914/2006). If a subject requests destruction of their blood samples and the samples have not yet been de-identified, Kadmon will destroy the samples as described in this FDA guidance. Kadmon will notify the investigator in writing that the samples have been destroyed.

## **15 CONDITIONS FOR MODIFYING THE PROTOCOL**

Protocol modifications to ongoing studies must be made only after consultation between a Kadmon representative and the investigator. Protocol modifications will be reviewed and approved by Kadmon representatives.

All protocol modifications must be submitted to the IRB for information and approval in accordance with local requirements, and to regulatory agencies if required. Approval must be obtained before any changes can be implemented, except for changes necessary to eliminate an immediate hazard to study subjects, or when the change involves only logistical or administrative aspects of the study (e.g., change in monitor, change of telephone number).

## **16 CONDITIONS FOR TERMINATING THE STUDY**

Kadmon has the right to terminate the study at any time. In terminating the study, Kadmon and the investigator will ensure that adequate consideration is given to the protection of the subjects' interests.

## **17 STUDY DOCUMENTATION, CRFS, AND RECORD KEEPING**

### **17.1 Investigator's Files and Retention of Documents**

The investigator must maintain adequate and accurate records to enable the conduct of the study to be fully documented and the study data to be subsequently verified. These documents should be classified into 2 separate categories as follows: (1) investigator's study files; and (2) subject clinical source documents.

The investigator's study file will contain the protocol and protocol amendments, eCRFs, IRB, and governmental approval with correspondence, sample ICF, drug records, staff curriculum vitae and authorization forms, and other appropriate documents and correspondence.

Subject clinical source documents (usually predefined by the project to record key efficacy and safety parameters independent of the eCRFs) may include subject hospital/clinic records, physician's and nurse's notes, appointment book, original laboratory reports, ECG, electroencephalogram, X-ray, pathology, and special assessment reports, signed ICFs, consultant letters, and subject screening and enrollment logs. The investigator must keep these 2 categories of documents on file for at least 2 years following the marketing application approval date for the study treatment and for the indication being investigated or for 2 years after the investigation is discontinued and the FDA notified. After that period of time, the documents may be destroyed subject to local regulations with prior written permission from Kadmon. If the investigator wants to assign the study records to another party or move them to another location, Kadmon must be notified in advance.

If the investigator cannot guarantee the archiving requirement at the study site for any or all of the documents, special arrangements must be made between the investigator and Kadmon to store these in a sealed container outside of the study site so that they can be returned sealed to the investigator in case of a regulatory audit. When source documents are required for the continued care of the subject, appropriate copies should be made for storing outside of the study site.

### **17.2 Source Documents and Background Data**

Upon request, the investigator will supply Kadmon with any required background data from the study documentation or clinic records. In case of special problems or governmental queries or

requests for audit inspections, it is also necessary to have access to the complete study records, provided that subject confidentiality is protected.

### **17.3 Audits and Inspections**

The investigator should understand that source documents for this study should be made available to appropriately qualified personnel from the Kadmon Quality Assurance Unit (or designee), or to health authority inspectors after appropriate notification. The verification of the eCRF data must be by direct inspection of source documents.

### **17.4 Electronic Case Report Forms**

Clinical study data for this study will be captured on eCRF. The investigator agrees to provide all information requested on the eCRF in an accurate manner according to instructions provided. eCRFs are designed for computer processing and analysis. The investigator should ensure the accuracy, completeness, and timeliness of the data reported to Kadmon in the eCRF and in all required reports.

An eCRF is required to be submitted for every subject who receives any amount of study drug. This includes submission of retrievable data on subjects who withdraw before completion of the study. If a subject stops treatment or terminates from the study, the dates and reasons must be noted on the eCRF.

## **18 MONITORING THE STUDY**

It is understood that the responsible Kadmon monitor (or designee) will contact and visit the investigator regularly and will be allowed on request to inspect the various records of the study (eCRFs and other pertinent data), provided that subject confidentiality is maintained in accordance with local requirements.

It will be the monitor's responsibility to inspect the eCRFs at regular intervals throughout the study, to verify the adherence to the protocol and the completeness, consistency, and accuracy of the data being entered on them. The monitor should have access to laboratory test reports and other subject records needed to verify the entries on the eCRF. The investigator (or designee) must agree to cooperate with the monitor to ensure that any problems detected in the course of these monitoring visits are resolved.

## **19 CONFIDENTIALITY OF STUDY DOCUMENTS AND SUBJECT RECORDS**

The investigator must ensure that subjects' anonymity will be maintained and that their identities are protected from unauthorized parties. On eCRFs or other documents submitted to Kadmon, subjects should be identified by an identification code and not by their names. The investigator should keep a subject enrollment log showing codes, names, and addresses. The investigator should maintain documents not for submission to Kadmon (e.g., subjects' written consent forms) in strict confidence.

## **20 PUBLICATION OF DATA AND PROTECTION OF TRADE SECRETS**

The results of this study may be published or presented at scientific meetings. The investigator agrees to submit all manuscripts or abstracts to Kadmon for review at least 30 days before submission. This allows Kadmon to protect proprietary information and to provide comments based on information from other studies that may not yet be available to the investigator.

In the event that Kadmon coordinates a publication or presentation of study results from all study sites, the participation of investigator or other representatives of study site as a named author shall be determined in accordance with Kadmon policy and generally accepted standards for authorship.

**Appendix A: Tables for Grading Laboratory Abnormalities**

The laboratory values provided in the tables below serve as guidelines and are dependent upon institutional normal parameters. Institutional normal reference ranges should be provided to demonstrate that they are appropriate.

Note: For LFT and bilirubin abnormalities, see Table 9-2 in Section 9.4.

Chemistry*	Mild (Grade 1)	Moderate (Grade 2)	Severe (Grade 3)	Potentially Life Threatening (Grade 4)**
Sodium – Hyponatremia mEq/L	132 – 134	130 – 131	125 – 129	< 125
Sodium – Hypernatremia mEq/L	144 – 145	146 – 147	148 – 150	> 150
Potassium – Hyperkalemia mEq/L	5.1 – 5.2	5.3 – 5.4	5.5 – 5.6	> 5.6
Potassium – Hypokalemia mEq/L	3.5 – 3.6	3.3 – 3.4	3.1 – 3.2	< 3.1
Glucose – Hypoglycemia mg/dL	65 – 69	55 – 64	45 – 54	< 45
Glucose – Hyperglycemia Fasting – mg/dL Random – mg/dL	100 – 110 110 – 125	111 – 125 126 – 200	>125 >200	Insulin requirements or hyperosmolar coma
Blood Urea Nitrogen BUN mg/dL	23 – 26	27 – 31	> 31	Requires dialysis
Creatinine – mg/dL	1.5 – 1.7	1.8 – 2.0	2.1 – 2.5	> 2.5 or requires dialysis
Calcium – hypocalcemia mg/dL	8.0 – 8.4	7.5 – 7.9	7.0 – 7.4	< 7.0
Calcium – hypercalcemia mg/dL	10.5 – 11.0	11.1 – 11.5	11.6 – 12.0	> 12.0
Magnesium – hypomagnesemia mg/dL	1.3 – 1.5	1.1 – 1.2	0.9 – 1.0	< 0.9
Phosphorous – hypophosphatemia mg/dL	2.3 – 2.5	2.0 – 2.2	1.6 – 1.9	< 1.6
CPK – mg/dL	1.25 – 1.5 × ULN***	1.6 – 3.0 × ULN	3.1 – 10 × ULN	> 10 × ULN
Albumin – Hypoalbuminemia g/dL	2.8 – 3.1	2.5 – 2.7	< 2.5	--
Total Protein – Hypoproteinemia g/dL	5.5 – 6.0	5.0 – 5.4	< 5.0	--

Chemistry*	Mild (Grade 1)	Moderate (Grade 2)	Severe (Grade 3)	Potentially Life Threatening (Grade 4)**
Cholesterol	201 – 210	211 – 225	> 226	---
Pancreatic enzymes – amylase, lipase	1.1 – 1.5 × ULN	1.6 – 2.0 × ULN	2.1 – 5.0 × ULN	> 5.0 × ULN

\*The laboratory values provided in the tables serve as guidelines and are dependent upon institutional normal parameters. Institutional normal reference ranges should be provided to demonstrate that they are appropriate.

\*\* The clinical signs or symptoms associated with laboratory abnormalities might result in characterization of the laboratory abnormalities as Potentially Life Threatening (Grade 4). For example, a low sodium value that falls within a grade 3 parameter (125-129 mEq/L) should be recorded as a grade 4 hyponatremia event if the subject had a new seizure associated with the low sodium value.

\*\*\*ULN\*\* is the upper limit of the normal range.

Hematology *	Mild (Grade 1)	Moderate (Grade 2)	Severe (Grade 3)	Potentially Life Threatening (Grade 4)
Hemoglobin (Female) - gm/dL	11.0 – 12.0	9.5 – 10.9	8.0 – 9.4	< 8.0
Hemoglobin (Female) change from baseline value - gm/dL	Any decrease – 1.5	1.6 – 2.0	2.1 – 5.0	> 5.0
Hemoglobin (Male) - gm/dL	12.5 – 13.5	10.5 – 12.4	8.5 – 10.4	< 8.5
Hemoglobin (Male) change from baseline value - gm/dL	Any decrease – 1.5	1.6 – 2.0	2.1 – 5.0	> 5.0
WBC Increase - cell/mm 	10,800 – 15,000	15,001 – 20,000	20,001 – 25,000	> 25,000
WBC Decrease - cell/mm 	2,500 – 3,500	1,500 – 2,499	1,000 – 1,499	< 1,000
Lymphocytes Decrease - cell/mm 	750 – 1,000	500 – 749	250 – 499	< 250
Neutrophils Decrease - cell/mm 	1,500 – 2,000	1,000 – 1,499	500 – 999	< 500
Eosinophils - cell/mm 	650 – 1500	1501 - 5000	> 5000	Hypereosinophilic
Platelets Decreased - cell/mm 	125,000 – 140,000	100,000 – 124,000	25,000 – 99,000	< 25,000
PT – increase by factor (prothrombin time)	1.0 – 1.10 × ULN**	1.11 – 1.20 × ULN	1.21 – 1.25 × ULN	> 1.25 ULN
PTT – increase by factor (partial thromboplastin time)	1.0 – 1.2 × ULN	1.21 – 1.4 × ULN	1.41 – 1.5 × ULN	> 1.5 × ULN
Fibrinogen increase - mg/dL	400 – 500	501 – 600	> 600	--

Hematology *	Mild (Grade 1)	Moderate (Grade 2)	Severe (Grade 3)	Potentially Life Threatening (Grade 4)
Fibrinogen decrease - mg/dL	150 – 200	125 – 149	100 – 124	< 100 or associated with gross bleeding or disseminated intravascular coagulation (DIC)

\* The laboratory values provided in the tables serve as guidelines and are dependent upon institutional normal parameters. Institutional normal reference ranges should be provided to demonstrate that they are appropriate.

\*\* “ULN” is the upper limit of the normal range.

Urine *	Mild (Grade 1)	Moderate (Grade 2)	Severe (Grade 3)	Potentially Life Threatening (Grade 4)
Protein	Trace	1+	2+	Hospitalization or dialysis
Glucose	Trace	1+	2+	Hospitalization for hyperglycemia
Blood (microscopic) – red blood cells	1 - 10	11 – 50	> 50 and/or gross blood	Hospitalization or packed red blood cells (PRBC) transfusion

\* The laboratory values provided in the tables serve as guidelines and are dependent upon institutional normal parameters. Institutional normal reference ranges should be provided to demonstrate that they are appropriate.

Food and Drug Administration (FDA). Guidance for Industry. Toxicity Grading Scale for Healthy Adult and Adolescent Volunteers Enrolled in Preventive Vaccine Clinical Trials. US Department of Health and Human Services, Center for Biologics Evaluation and Research. September 2007.

**Appendix B: Correction for Heart Rate (Fridericia)\***

The following formula will be used to correct to QT interval:

$$QT_F = \frac{QT}{RR^{1/3}}$$

Where  $QT_F$  is the QT interval corrected for heart rate, and RR is the cube root of the interval from the onset of 1 QRS complex to the onset of the next QRS complex.

\*Fridericia LS (1920). "The duration of systole in the electrocardiogram of normal subjects and of patients with heart disease." *Acta Medica Scandinavica*. (53): 469–486.

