### 6.3 Exclusion Criteria

Any subject who meets any of the following criteria will be ineligible for participation in the study:

1. Non-plaque or drug-induced (antimalarials, lithium) psoriasis (if subject is taking angiotensin II receptor blockers or beta blockers, doses must be stable for 6 months prior to study entry)
2. Use of systemic corticosteroid within 12 weeks prior to study entry
3. Use topical corticosteroids except to the face, groin, or scalp
4. Use of methotrexate, retinoids (such as acitretin), or calcineurin inhibitors (such as cyclosporine) within 4 weeks prior to study entry
5. Phototherapy within 4 weeks prior to study entry
6. Biologic therapies, including antibodies to IL-17, anti-TNF $\alpha$ , anti-IL-12 and IL-23, within 3 months prior to study entry
7. Current use of an inhibitor, inducer, or CYP3A4 (see Appendix G)
8. Active viral, fungal, or bacterial skin infection (other than nail fungal infection)
9. Is a pregnant or lactating woman
10. History of GI surgery including any bariatric surgery, or any GI condition that might interfere with drug absorption
11. Current participation in another study with an investigational drug or within 28 days or 5 half-lives of the investigational drug (whichever is longer) of study entry
12. History or other evidence of severe illness or any other conditions that would make the subject, in the opinion of the investigator, unsuitable for the study
13. Has QTc(F) interval (QT interval data corrected using Fridericia's formula) of > 450 msec (average of 3 readings) during screening (Appendix B)

14. Regular and/or excessive use of alcohol within the 2 years prior to study entry defined as alcohol intake > 14 drinks per week in a man or > 7 drinks per week in a woman. Approximately 10 g of alcohol equals one “drink” unit. One unit equals 1 ounce of distilled spirits, one 12-ounce beer, or one 4-ounce glass of wine.
15. Exposure to KD025 within the last 6 months prior to study entry, or known allergy/sensitivity to KD025 or any other ROCK-2 inhibitor
16. History or presence of any of the following:
  - a. ALT or AST >  $2.0 \times$  ULN at screening. (Subjects with an isolated AST elevation of any magnitude, or a ratio of AST:ALT > 1.5 should be interviewed regarding use of alcohol, have levels repeated and participation in the study should be discussed with the medical monitor.)
  - b. Renal disease and/or serum creatinine >  $1.5 \times$  ULN at screening

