#### **7.2.5 12-Lead Electrocardiogram**

Supine 12-lead ECGs will be obtained prior to blood sample collection (tolerance window: -240 minutes to 0 hour).

Digital 12-lead ECG measurements are to be taken with the subject in a supine position and having rested in this position for at least 5 minutes before each reading. The ECG is to be repeated 3 times consecutively within 30 minutes (with a required interval of at least 1 to 2 minutes between ECGs). At each visit, and when possible, the ECG is to be performed immediately prior to any blood sample collection.

The following ECG parameters will be collected: PR interval, RR interval, QRS interval, QT interval, and QTc interval (QTc[F]; Fridericia's correction, see Appendix B for formula). The ECG findings will be evaluated by a qualified physician for the presence of abnormalities (qualitative assessment). The physician will assess each ECG as normal, abnormal/not clinically significant, or abnormal/clinically significant.

Abnormalities in the ECG that lead to a change in subject management (e.g., dose interruption or delay, requirement for additional medication or monitoring) or result in clinical signs and symptoms are considered clinically significant for the purposes of this study and will be recorded on the AE eCRF. If ECG abnormalities meet criteria defining them as serious, they must be reported as an SAE (see Section 11.3.1).

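### Protocol Appendix B defines RR as already a cube root, so its QTcF formula, applied literally, makes only one third of the intended heart-rate correction

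*Protocol*

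**What the plan says.** Protocol Appendix B displays the correction as QT divided by RR to the power 1/3, under a heading that names Fridericia. The line below the formula defines its terms and states that "RR is the cube root of the interval from the onset of 1 QRS complex to the onset of the next QRS complex". It gives no unit for RR.

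Two parts of the protocol body rely on this appendix:

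- Section 6.3, exclusion 13, bars subjects whose screening QTcF, averaged over three readings, is above 450 msec, and cites Appendix B. The synopsis gives the same criterion without the citation.
- Section 7.2.5 names Fridericia's correction and adds "see Appendix B for formula". It lists the parameters to be collected as "PR interval, RR interval, QRS interval, QT interval, and QTc interval", so RR is treated there as an interval.

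SAP 3.9.4 prints the same expression, QT/RR^(1/3). It neither defines RR nor states a unit. It tabulates QTcF in categories with cut-points at 450, 480 and 500 ms, and change from baseline with cut-points at 0, 30 and 60 ms.

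**The concern.** The formula already takes the cube root of RR. If RR is itself the cube root of the interval, the root is taken twice. Nothing else in the protocol corrects the sentence, and it reads as an intact statement rather than as damaged text.

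Appendix B is the named source of the formula behind a cardiac-safety exclusion. A QTcF derived from its definition would be compared with 450 msec on the wrong scale. It would also differ from the value for the same ECG under SAP 3.9.4, if RR there is read as the interval. Averaging three readings would not help, because all three would carry the same error.

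**Working it through.** **Inputs from the documents.** The displayed formula and the definition of RR (Appendix B); the 450 msec limit (exclusion 13); RR listed as an interval (Section 7.2.5); the SAP expression (SAP 3.9.4). No worked QTcF value is given, so there is no stated figure to reproduce.

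**Assumed inputs.** RR in seconds, taken as 60/heart rate, and the QT and heart-rate values below. None of these is in the documents.

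**Algebra (no assumption needed).** Let I be the interval between QRS onsets.

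- RR as the interval: QTcF = QT / I^(1/3).
- RR as Appendix B defines it: RR = I^(1/3), so QTcF = QT / (I^(1/3))^(1/3) = QT / I^(1/9).
- On the log scale the correction is (1/9) ln I instead of (1/3) ln I. The ratio is (1/9)/(1/3) = 1/3.
- Literal value divided by intended value = I^(1/3 − 1/9) = I^(2/9). With I in seconds, this is below 1 when the heart rate exceeds 60 bpm, equal to 1 at 60, and above 1 below 60.

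**Examples (assumed QT and heart rate).**

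| QT, heart rate | I (s) | RR as the interval | As written |
|---|---|---|---|
| 400 ms, 90 bpm | 0.667 | 400/0.667^(1/3) = 457.9 | 400/0.667^(1/9) = 418.4 |
| 420 ms, 80 bpm | 0.750 | 420/0.750^(1/3) = 462.3 | 420/0.750^(1/9) = 433.6 |
| 400 ms, 60 bpm | 1.000 | 400.0 | 400.0 |
| 440 ms, 50 bpm | 1.200 | 440/1.2^(1/3) = 414.1 | 440/1.2^(1/9) = 431.2 |
| 460 ms, 50 bpm | 1.200 | 460/1.2^(1/3) = 432.9 | 460/1.2^(1/9) = 450.8 |

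The first two rows move from above 450 to below it, and the last moves from below to above. The fourth row changes the value but not the eligibility decision.

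**Range at the limit.** The literal reading when the intended QTcF is exactly 450 ms is 450 × I^(2/9):

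| Heart rate (bpm) | 45 | 50 | 60 | 70 | 80 | 90 | 100 |
|---|---|---|---|---|---|---|---|
| Literal value (ms) | 479.7 | 468.6 | 450.0 | 434.8 | 422.1 | 411.2 | 401.7 |

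Conversely, a literal value of 450 ms corresponds to an intended QTcF of 479.7 ms at 80 bpm and 492.4 ms at 90 bpm.

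**Unit.** If RR were entered in milliseconds (750 at 80 bpm), QT 400 would give 44.0 with RR as the interval and 191.7 as written. Neither is plausible against a 450 msec limit, so the missing unit is secondary and likely to be noticed. The doubled root is not: it gives values that look ordinary.

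**The case against.** The best defence is that this is a slip in one explanatory sentence. The displayed formula is right, the method is named as Fridericia's wherever QTcF is mentioned, and Section 7.2.5 collects RR as an interval. The sentence probably meant to describe the denominator, which is indeed a cube root. All of this stands, and it limits the severity. It does not make the definition correct, and the appendix is cited for an eligibility limit.

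Three stronger readings are tempting, and the documents do not support them.

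- A reader might infer that sites are told to calculate QTcF by hand from Appendix B, and so that ineligible subjects were enrolled. Section 7.2.5 calls for digital ECG measurements and lists QTc among the collected parameters; the appendix is a cross-reference for the formula. No section says how QTcF is derived. Misclassification needs someone to follow the definition in preference to the printed formula and the named method.
- A reader might infer that the protocol and the SAP use different formulas. The two displayed expressions are the same; only the protocol's definition of RR departs from it. The SAP is not a full model for the repair either, because it gives neither a definition nor a unit.
- A reader might infer that the SAP's QTcF tables are wrong. They are unaffected if RR is read there as the interval.

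It is also fair to say that the examples are chosen to show values crossing 450 msec. The documents give no distribution of QT or heart rate, so the number of screened subjects who could be affected cannot be estimated.

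**Conclusion.** Wrong as written, low severity. That the root is doubled follows from the text of Appendix B alone. The size in milliseconds rests on RR in seconds and on assumed heart rates: at an intended QTcF of 450 ms, the literal value is about 15 ms too low at 70 bpm (450 − 434.8 = 15.2), about 39 ms too low at 90 bpm (450 − 411.2 = 38.8), and about 19 ms too high at 50 bpm (468.6 − 450 = 18.6). The error can therefore cross the exclusion limit in either direction, but only for values derived from the literal definition. Whether any were is unknown from the documents.

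**What to change.** - In Appendix B, remove the reference to a cube root from the definition, so that RR is the interval, in seconds, from the onset of one QRS complex to the onset of the next. Leave the displayed formula as it is.
- Add the same definition and unit to SAP 3.9.4, which has neither.
- Confirm how screening QTcF was obtained. Where any value was calculated from Appendix B, check that it used the interval itself, and recompute it from the recorded QT and RR if it did not.

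The 450 msec limit and the SAP's QTcF categories stay as they are. The cost is one sentence in each document, plus a check of screening values only if some were calculated from the appendix.
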